6.15.2. Safety Subgroup Analyses

Subgroup analysis for safety related endpoints will be performed within the context of the integrated safety analysis. No safety subgroup analysis will be performed specifically for this study unless there is a potentially relevant finding during the periodic study safety reviews.

6.16. Protocol Deviations

Protocol deviations will be identified throughout the study. Important protocol deviations are defined as those deviations from the protocol likely to have a significant impact on the completeness, accuracy, and/or reliability of the study data or that may significantly affect a patient's rights, safety, or well-being.

Potential examples of important protocol deviations include patients who violated the inclusion/exclusion criteria, used an interfering concomitant medication, significant non-compliance with study medication (<75% of expected injections). Refer to a separate document called "KGAB Trial Issues Management Plan" for the important protocol deviations with categorizations.

The number and percentage of patients having IPD(s) will be summarized within category and subcategory of deviation by treatment group for Induction Period using the ITT population and for Maintenance Period using all the Maintenance Populations (including Maintenance Primary Population, Maintenance Secondary Population, and Maintenance W16 Escape Population).

A by-patient listing of important protocol deviations will be provided for the ITT population.

6.16.1. Impact of COVID-19

Impact of pandemic (e.g., COVID-19) on analyses may be addressed prior to study unblinding at Week 16 DBL, once the impact on study conducts are fully understood. In general, any missing assessments/visit window will be documented as protocol deviations. For patients who have

missing assessments at Week 16 due to COVID-19, these patients may enter the escape arm. A summary or listing may be provided to summarize missing visits due to COVID-19.

Treatment discontinuation due to pandemic will be treated the same type of intercurrent event as treatment discontinuation due to reasons other than lack of efficacy. Strategies of how this type of intercurrent event will be handled are described in Section 6.2. Intermittent missing assessment due to pandemic will be treated the same as any other intermittent missing values. Details of how missing data will be handled are described in Section 6.4.

6.17. Interim Analyses and Data Monitoring

Data Monitoring Committee/Data Safety Monitoring Board (DMC/DSMB): The lebrizumab Phase 3 AD programs' DSMB is an independent expert advisory group commissioned and charged with the responsibility of evaluating cumulative safety at regular intervals, as well as on an ad hoc basis, as needed. The DSMB will consist of members external to Lilly and follow the rules defined in the DSMB charter, focusing on potential and identified risks for this molecule. Data Monitoring Committee membership will include, at a minimum, a physician with expertise in dermatology and a statistician. No member of the DSMB may have contact with study sites. This committee will make recommendations as to a) continue the clinical studies without modification; or b) continue the clinical studies with modifications; or c) terminate one or more of the clinical studies. Details outlining the roles and responsibilities of the DMC are documented in the "Dermira DRM06 DSMB Program Charter" and the planned analyses are outlined in the DMC analysis plan prior to the first unblinded assessment.

Access to the unblinded safety data will be limited to the DSMB. The study team will not have access to the unblinded data. Only the DSMB is authorized to evaluate unblinded data. The purpose of the DSMB is to advise Lilly regarding patient safety; however, the DSMB may request key efficacy data to put safety observations into context and to confirm a reasonable benefit/risk profile for ongoing patients in the study. Hence, there will be no alpha adjustment for these interim assessments.

Week 16 Database lock (DBL): An unblinded interim analysis will be performed at the time (i.e., a cut-off date) the last patient completes Week 16 or the ETV from the study. This database lock will include all data collected by the cut-off date. Only the Induction Period treatment assignment will be unblinded at the time of this interim lock. Maintenance Period treatment assignment will remain blinded.

Week 52 DBL: Another unblinded interim analysis will be performed at the time (that is, a cut-off date) the last patient completes Week 52 or the ETV from the study. This database lock will include all data collected by the cut-off date and is the final analysis for the efficacy endpoints up to Week 52.

The study will not be terminated early on the basis of efficacy following these interim analyses.

Final DBL: A final DBL will occur after all patients have completed the safety follow-up period of the study, discontinued current study, or enrolled into the long-term extension study DRM06-AD07.

Depending on the regulatory submission timeline, the Week 52 DBL and the final DBL may be combined, that is, one final DBL will occur after all patients have either completed the follow-up period of the study discontinued the study early, or entered the long-term extension study DRM06-AD07.

6.18. Annual Report Analyses

Based on regulatory requirements for the Development Safety Update Report (DSUR), reports will be produced (if not already available from the study CSR) for the reporting period covered by the DSUR.

Appendix 1. Study Visit Mapping for Pruritus NRS and Sleep-loss Diary and POEM

Pruritus NRS and sleep loss are collected as a daily diary; entries will be mapped to study week by the following:

Week	Start Day	End Day
Baseline	Date of First Injection ^a - 7	Date of First Injection-1
Week 1	Max(Date of First Injection, Week 2 Visit Date - 14)	Week 2 Visit Date - 8
Week 2	Week 2 Visit Date - 7	Week 2 Visit Date - 1
Week 4	Week 4 Visit Date - 7	Week 4 Visit Date - 1
Week 6	Week 6 Visit Date - 7	Week 6 Visit Date - 1
Week 8	Week 8 Visit Date - 7	Week 8 Visit Date - 1
Week 10	Week 10 Visit Date - 7	Week 10 Visit Date - 1
Week 12	Week 12 Visit Date - 7	Week 12 Visit Date - 1
Week 14	Week 14 Visit Date - 7	Week 14 Visit Date - 1
Week 16	Week 16 Visit Date - 7	Week 16 Visit Date - 1
Week 20	Week 20 Visit Date - 7	Week 20 Visit Date - 1
Week 24	Week 24 Visit Date - 7	Week 24 Visit Date - 1
Week 28	Week 28 Visit Date - 7	Week 28 Visit Date - 1
Week 32	Week 32 Visit Date - 7	Week 32 Visit Date - 1
Week 36	Week 36 Visit Date - 7	Week 36 Visit Date - 1
Week 40	Week 40 Visit Date - 7	Week 40 Visit Date - 1
Week 44	Week 44 Visit Date - 7	Week 44 Visit Date - 1
Week 48	Week 48 Visit Date - 7	Week 48 Visit Date - 1
Week 52	Week 52 Visit Date - 7	Week 52 Visit Date - 1

^a If date of first injection is missing, the randomization date will be used.

If multiple assessments on a single day are present, use the first assessment. If an assessment could be mapped to different weeks, it will be mapped to the earlier week. Derivation of the weekly mean scores for Pruritus NRS and Sleep-loss could be found in [Table KGAB.6.11](#). If at least 1 of the 7 days contains non-missing daily assessments, post-baseline weekly score will be calculated using prorated weekly average. If the range of 7 days are all missing daily assessments, then the weekly score is missing.

POEM are collected every week via eDiary, the visit week mapping will follow the following rule: the last collected POEM data before the visit date would be used, the evaluation window is

injection date - 7 to injection date -1 for baseline and assessment date - 7 to assessment date -1 for post baseline. For example if a patient gets an injection/assessment on the 14th, we would use the scale completed in between of the 13th and the 7th.

Appendix 2. Details of Combining Estimates and Test Statistics for Categorical Endpoints with Multiple Imputation

Following the implementation of MCMC-MI imputation as specified in Section 6.4.1.1, the 25 data sets with imputations should be set together and sorted by imputation number. The following sections describe the processes for combining inferences for the individual imputed data sets into one inference for reporting. All calculations are performed in SAS software version 9.4.

Summarize Unadjusted Response Rate

The response rates, overall and by treatment arm, and their associated standard errors (SE) are computed for each imputed data set using PROC FREQ with the *riskdiff* option specified for the appropriate column in the TABLES statement. The response rates and SEs from the resulting output are combined across the 25 imputed data sets using PROC MIANALYZE, separately for each arm and the overall group.

Note that the estimate and 95% confidence interval (CI) bounds output by PROC MIANALYZE are percents (i.e., they are in terms of the response rate). To obtain the number of responders, the estimated percent is multiplied by the number of individuals in the analysis population and rounded to the nearest integer.

Compute Stratified Measures of Association

The common risk difference, common odds ratio (OR), and Cochran-Mantel-Haenszel (CMH) test statistic are computed for each imputed data set using PROC FREQ with the *riskdiff* option for the appropriate column (for risk difference) and the *cmh* option (for odds ratio and CMH test statistic) specified in the TABLES statement. Each of these analyses are stratified by geographic region, age group, and baseline disease severity via inclusion of these variables in the TABLES statement with the treatment and outcome variables.

Note that the PROC FREQ output corresponding to the Mantel-Haenszel method is used for the risk difference, and the output corresponding to the General Association statistic is used for the CMH statistic. PROC MIANALYZE is then called separately for each of these measures, with further details in the sections below.

Common Risk Difference

No transformation is necessary before using PROC MIANALYZE to combine the risk difference estimates and their associated SEs across the 25 imputed data sets. This procedure outputs an estimate of the common risk difference and the associated 95% CI bounds.

Common Odds Ratio

The OR from each imputed data set is first transformed using the natural logarithm. The SE for each log OR ($SE_{\log OR}$) is derived from the OR 95% CI bounds (LB_{OR} , UB_{OR}) according to the

following equation: $SE_{\log OR} = (\ln(UB_{OR}) - \ln(LB_{OR})) / (2 * 1.96)$. The log OR and derived SE are then combined using PROC MIANALYZE, which outputs a combined estimate of the log OR and the associated 95% CI. Finally, these measures can be exponentiated to transform them back to the OR scale.

Cochran-Mantel-Haenszel Test

The CMH test statistic (CMH) from each imputed data set is transformed using the Wilson-Hilferty transformation and standardized so that it has approximately a standard Normal distribution (Ratitch 2013). In particular, the transformed CMH statistic is computed as follows:

$$CMH_{WH} = \frac{\left(\frac{CMH}{df}\right)^{\frac{1}{3}} - \left(1 - \frac{2}{9 * df}\right)}{\sqrt{\frac{2}{9 * df}}}$$

where df is the degrees of freedom of the CMH statistic. Then the

SE for each CMH_{WH} is 1, and PROC MIANALYZE is used to output a combined estimate of the transformed CMH statistic. Note that the two-sided p-value output by PROC MIANALYZE is not used directly, but instead the one-sided p-value is computed manually using both the t statistic and two-sided p-value output by PROC MIANALYZE: if t statistic is greater than 0, then one-sided p-value is computed as half of the two-sided p-value; otherwise, the one-sided p-value is computed as 1 - half of the two-sided p-value. The resulting one-side p-value is reported as the pooled p-value for the CMH test.

Appendix 3. Definition of Rescue Medications

This appendix provides the definition of rescue medications for this study, including topical and systemic treatments defined as following:

1. Topical Atopic Dermatitis Treatment (including topical corticosteroids, TCI and crisaborole)

Route of topical treatments includes: Topical and Transdermal.

Topical Corticosteroids (TCS): ATC code is D07

High Potency TCS: ATC codes: D07AC or D07AD

Low or moderate potency TCS: ATC code is D07, excluding D07AC or D07AD

Topical calcineurin inhibitor (TCI): Preferred Term includes: TACROLIMUS, PIMECROLIMUS

Crisaborole: Preferred Term includes: CRISABOROLE

2. Systemic Atopic Dermatitis Treatment (including systemic corticosteroids, immunosuppressant, biologics and phototherapy/photochemotherapy)

Route of systemic treatments administration includes: Oral, Intra-Arterial, Intramuscular, Intraperitoneal, Intravenous, Subcutaneous, Transdermal. (This condition applies to the following categories except for phototherapies.)

Systemic Corticosteroids: ATC code is H02

Immunosuppressant: Defined as: ATC2 is L04 or Preferred terms of Abrocitinib or Ruxolitinib

Biologics: Defined as following Preferred terms:

Infliximab, Infliximabum, Etanercept, Etanerceptum, Adalimumab, Adalimumabum, Certolizumab, Certolizumabum, Certolizumab pegol, Golimumab, Golimumabum, Ozoralizumab, Afelimomab, Afelimomabum, Tumor Necrosis Factor Alpha (TNF-) Inhibitors, Tabalumab, Tregalizumab, Anakinra, Basiliximab, Basiliximabum, Daclizumab, Daclizumabum, Tocilizumab, Tocilizumabum, Mepolizumab, Mepolizumabum, Rilonacept, Rilonaceptum, Ustekinumab, Canakinumab, Briakinumab, Fezakinumab, Sirukumab, Sarilumab, Lebrikizumab, Secukinumab, Olokizumab, Gevokizumab, Brodalumab, Ladarixin, Ixekizumab, Dupilumab, Tildrakizumab, Tildrakizumabum, Reslizumab, Reslizumabum, Guselkumab, Guselkumabum, Olamkicept, Fletikumab, Bimekizumab, Mirikizumab, Risankizumab, Abatacept, Ligelizumab, Vedolizumab, Belimumab, Nemolizumab, Tralokinumab, Omalizumab

Phototherapy or Photochemotherapy:

Programming search of medication name (actual term or preferred term) contains 'photo' then medicals to manually review to confirm whether the medication in question is indeed 'Phototherapy' or 'Photochemotherapy'

Signature Page for VV-CLIN-015695 v1.0

Approval	PPD an 21-Mar-2022 11:46:59 GMT+0000
----------	--

Signature Page for VV-CLIN-015695 v1.0

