## 4.2. Exclusion Criteria

Patients meeting any of the criteria below will be excluded from this study:

1. Participation in a prior lebrikizumab clinical study.
2. History of anaphylaxis as defined by the Sampson criteria (Sampson, 2006).
3. Treatment with topical corticosteroids, calcineurin inhibitors or phosphodiesterase-4 inhibitors such as crisaborole within 1 week prior to the baseline visit.
4. Prior treatment with dupilumab or tralokinumab.
5. Treatment with any of the following agents within 4 weeks prior to the baseline visit:
  - a. Immunosuppressive/immunomodulating drugs (e.g., systemic corticosteroids, cyclosporine, mycophenolate-mofetil, IFN- $\gamma$ , Janus kinase inhibitors, azathioprine, methotrexate, etc.)
  - b. Phototherapy and photochemotherapy (PUVA) for AD.
6. Treatment with the following prior to the baseline visit:
  - a. An investigational drug within 8 weeks or within 5 half-lives (if known), whichever is longer.
  - b. B Cell-depleting biologics, including rituximab, within 6 months.
  - c. Other biologics within 5 half-lives (if known) or 16 weeks, whichever is longer.
7. Use of prescription moisturizers within 7 days of the baseline visit.
8. Regular use (more than 2 visits per week) of a tanning booth/parlor within 4 weeks of the screening visit.
9. Treatment with a live (attenuated) vaccine within 12 weeks of the baseline visit or planned during the study.
10. Uncontrolled chronic disease that might require bursts of oral corticosteroids, e.g., co-morbid severe uncontrolled asthma (defined by an ACQ-5 score  $\geq 1.5$  or a history of  $\geq 2$  asthma exacerbations within the last 12 months requiring systemic [oral and/or parenteral] corticosteroid treatment or hospitalization for  $> 24$  hours).
11. Active chronic or acute infection requiring treatment with systemic antibiotics, antivirals, antiparasitics, antiprotozoals, or antifungals within 2 weeks before the baseline visit, or superficial skin infections within 1 week before the baseline visit.  
NOTE: patients may be rescreened after infection resolves.
12. Evidence of active acute or chronic hepatitis (as defined by the Department of Health & Human Services Centers for Disease Control and Prevention) or known liver cirrhosis.
13. Diagnosed active endoparasitic infections or at high risk of these infections.

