### **6.3. Rescue Treatment for Atopic Dermatitis**

#### **Induction Period**

The use of topical or systemic treatments for atopic dermatitis is prohibited from Baseline through Week 16 in this study. Patients who experience intolerable AD symptoms and require treatment should, preferably, be started on topical treatments (e.g., mid-potency TCS) prior to instituting systemic treatments for AD symptoms, in accordance with best practice.

If systemic rescue treatments (e.g., oral corticosteroids, phototherapy, cyclosporin, etc.) are required, study drug must be discontinued. The patient should continue to attend all study visits through Week 16 and be assessed for safety and efficacy according to the schedule of events.

Patients requiring topical or systemic rescue medication who complete the study through Week 16 will be eligible to continue to the Escape Arm after the Week 16 visit has been completed. Patients who required systemic rescue medication must wait for rescue medication washout ( $\geq 5$  half-lives of the medication) prior to entering the Escape Arm.

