6.2.1. Primary and Supportive Estimands for Induction Period

There will be three estimands of interest in analyzing primary and secondary endpoints for Induction Period. Two types of intercurrent events in terms of estimating the treatment effects for Induction Period will be considered, initiation of rescue medication as defined in Protocol Section 6.3 and permanent treatment discontinuation.

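### SAP Appendix 3 lists fewer rescue medications than Protocol Section 6.3 covers, so a user of an unlisted atopic dermatitis treatment can be analysed as an unrescued responder

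*SAP*

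**What the plan says.** **The rule the analyses cite.** SAP 6.2.1 names the induction intercurrent event as "initiation of rescue medication as defined in Protocol Section 6.3". SAP 6.4.1.1 (multiple imputation, for topical rescue) and 6.4.1.3 (non-responder imputation) point to the same protocol section. For Induction, Protocol 6.3 states: "The use of topical or systemic treatments for atopic dermatitis is prohibited from Baseline through Week 16 in this study". It gives examples of topical and systemic rescue but no closed list.

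**The list meant to implement it.** SAP Appendix 3 opens: "This appendix provides the definition of rescue medications for this study". SAP 6.10.1 refers to it for the definition, and the SAP revision history describes it as detailed instructions for identifying rescue medication.

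- Topical block, routes Topical and Transdermal: ATC D07, the terms tacrolimus and pimecrolimus, and "Crisaborole: Preferred Term includes: CRISABOROLE".
- Systemic block: "Route of systemic treatments administration includes: Oral, Intra-Arterial, Intramuscular, Intraperitoneal, Intravenous, Subcutaneous, Transdermal". This route condition applies to every category in the block except phototherapy.
- JAK inhibitors appear only in the systemic block: "Immunosuppressant: Defined as: ATC2 is L04 or Preferred terms of Abrocitinib or Ruxolitinib".

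**The protocol's wording on PDE-4 inhibitors.** Exclusion 3 in Protocol 4.2 uses a class term: "calcineurin inhibitors or phosphodiesterase-4 inhibitors such as crisaborole within 1 week prior to the baseline visit". Protocol 6.1 also refers to the class, with crisaborole as an example.

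**The concern.** The primary estimand (SAP 6.2.1.1) asks about response reached without rescue. It does this by resetting the scores of a rescued patient to baseline from the rescue onward. The flag that identifies rescue is therefore part of the endpoint definition. If the flag is built from Appendix 3 alone, a patient who used an unlisted AD treatment is not reset. The observed Week 16 IGA, EASI and itch scores stand, and a response achieved with that help counts as a response to randomised treatment.

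The same flag feeds non-responder imputation, the tipping-point analysis, the percentage rescued by visit, the flare definition and time to first rescue. In Maintenance, topical rescue is permitted and leads to scores set to missing (primary estimand) or to non-response (composite estimand). Unlisted topical use would escape both.

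**Working it through.** **1. Apply the list as written.** Each row takes a product and route as they might be recorded and checks them against both blocks of Appendix 3.

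| Recorded product and route | Topical block | Systemic block | Appendix 3 result | Protocol 6.3, Induction, if used for AD |
|---|---|---|---|---|
| D07 corticosteroid, Topical | match | – | flagged | rescue |
| Crisaborole, Topical | match | – | flagged | rescue |
| Another PDE-4 inhibitor, Topical | no term | route fails | **not flagged** | rescue |
| Ruxolitinib or an L04 agent other than the two listed calcineurin inhibitors, Topical | no term | term matches, route fails | **not flagged** | rescue |
| Ruxolitinib, Transdermal | no term | term and route match | flagged as systemic | rescue |
| Another PDE-4 inhibitor, oral | route fails | only if coded L04 (coding not given) | not determinable | rescue |

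Two rows are missed outright. The ruxolitinib case uses a drug term and a route value that Appendix 3 itself lists. Only the combination is absent.

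**2. Figures stated in the plan.** The plan gives no figure for rescue use. The nearest stated figure is the power in SAP 5.2: 96 versus 48 patients, 34.7% versus 7.7%, two-sided 0.05.

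- Formula: power = Φ[(Δ − 1.96·SE₀)/SE₁], with SE₀ from the pooled rate and SE₁ from the separate rates.
- Δ = 0.270. The pooled rate is (96 × 0.347 + 48 × 0.077)/144 = 0.257, so SE₀ = 0.0773 and SE₁ = 0.0620.
- Power = Φ(1.91) = 97.2%. With the continuity correction that the SAP names it is about 95.2%.

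The claim of more than 95% reproduces.

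**3. Size per patient, Induction.** About 400 patients at 2:1 gives 267 and 133.

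- Lebrikizumab: 1/267 = 0.37 percentage points per misclassified responder.
- Placebo: 1/133 = 0.75 percentage points.

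**4. Illustrative range.** Assume 0 to 5 misclassified responders in an arm. This is an assumption, because the documents give no frequency. The planning difference is 34.7 − 7.7 = 27.0 points.

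- 5 on lebrikizumab only: 27.0 + 5/267 (1.9) = 28.9 points.
- 5 on placebo only: 27.0 − 5/133 (3.8) = 23.2 points.
- 5 in each arm: 36.6 − 11.5 = 25.1 points.

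Power at 267:133 stays above 99.9% in all of these cases.

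**5. Size per patient, Maintenance.** Assume the planning rates (34.7% IGA, 48.0% EASI-75), 267 induction patients on lebrikizumab, one fifth of responders re-randomised to placebo, and no dropout.

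- IGA responders on placebo: 267 × 0.347/5 ≈ 19. One patient is about 5 points.
- EASI-75 responders on placebo: 267 × 0.480/5 ≈ 26. One patient is about 4 points.

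This applies to the composite estimand, where a flagged patient moves fully to non-response. Under the maintenance primary estimand the value would be imputed, so the shift would be smaller.

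**The case against.** The strongest reply is that the governing rule is already broad. The estimand and imputation texts cite Protocol 6.3, and read literally they would treat an unlisted topical user as rescued. The wording of Appendix 3 can also be read as giving examples. That stands as far as it goes: the SAP nowhere says that the list overrides Protocol 6.3, so misclassification can happen but is not certain. It does not remove the problem, because Appendix 3 also calls itself the definition and is built from codes, terms and routes. Someone following it exactly would leave these patients unflagged.

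A reader might infer several stronger things that the documents do not support:

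- **That JAK inhibitors are absent from the list.** They are in the systemic block, and ruxolitinib recorded as Transdermal would be flagged. The gap depends on how the route is recorded.
- **That the entry criteria show topical JAK products were meant to count.** Exclusion 5a names the class among immunosuppressive drugs and gives no route, which is silence and not evidence. The list in Protocol 6.1 concerns therapies introduced for other conditions. The comparison that matters is with Protocol 6.3.
- **That such products were available or used at these sites.** Nothing in the documents shows this.
- **That the gap favours lebrikizumab.** If unlisted use is as common or more common on placebo, the difference shrinks.

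Use would also not be invisible. Protocol 6.3 requires all AD treatments to be captured in the eCRF, concomitant medication is summarised (SAP 6.10), and interfering medication is a potential important deviation (SAP 6.16). None of these corrects the response flag.

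**Conclusion.** The point holds as a mismatch between two definitions of the main intercurrent event. Appendix 3 is narrower than the protocol section that the estimands cite, and applying it as written can classify a rescued patient as an unrescued responder.

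The effect is probably small. Each such patient moves an induction rate by 0.37 points (lebrikizumab) or 0.75 points (placebo). In the smaller re-randomised placebo group, one patient could move a composite maintenance rate by about 4 to 5 points under the assumptions shown. Frequency and direction are unknown. No figure in the plan is wrong and no stated power changes. What is at stake is whether the analysis estimates what the estimand describes, and that can be put right from data already collected.

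**What to change.** 1. State in SAP 6.2 and Appendix 3 that Protocol 6.3 governs and that the code list is a tool for applying it.
2. In Appendix 3 and SAP 6.10.1, replace the single crisaborole entry with PDE-4 inhibitors as a class. Include JAK inhibitors by any route, with Topical among the routes. Say whether a skin-applied JAK inhibitor counts as topical or systemic, because the maintenance primary estimand handles the two differently.
3. Add a medical review, by staff without access to treatment codes, of any other product recorded in the eCRF with AD as the indication. Appendix 3 already uses manual medical review for phototherapy.

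**Timing.** SAP Version 4 was approved after the study team was unblinded to induction treatment but before maintenance treatment was unblinded. The change can therefore be applied prospectively to Maintenance. For Induction it should be reported as a documented correction or as a supplementary analysis beside the result from the existing list.

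**Cost.** A few code-list entries and one pass through medication records that already carry route and indication. Response rates may fall slightly.

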**ACRONYMS**

Acronym	Term
ACQ-5	Asthma Control Questionnaire
AD	atopic dermatitis
ADA	anti-drug antibody
AE	adverse event
AESI	adverse event of special interest
ALT	alanine amino-transferase
ANCOVA	analysis of covariance
AST	aspartate amino-transferase
AUC	area under the curve
BP	blood pressure
BSA	body surface area
BUN	blood urea nitrogen
C	Celsius
CFR	Code of Federal Regulations
Cmax	maximum (or peak) serum concentration
DLQI/CDLQI	Dermatology Life Quality Index/Children's Dermatology Life Quality Index
DSMB	Data Safety Monitoring Board
EASI	Eczema Area and Severity Index
EASI-50	50% reduction in EASI from Baseline to Week 16
EASI-75	75% reduction in EASI from Baseline to Week 16
eCRF	electronic case report form
EDC	electronic data capture
EMA	European Medicines Agency
EQ-5D	standardized instrument developed by the EuroQol Group
ET	early termination
EU	European Union
F	Fahrenheit
FDA	Food and Drug Administration
FLG	filaggrin
GCP	good clinical practice
GGT	gamma-glutamyl transferase

Acronym	Term
HCT	hematocrit
HGB	hemoglobin
HIV	human immunodeficiency virus
ICF	informed consent form
ICH	International Conference on Harmonization
IEC	independent ethics committee
IFN	interferon
Ig	immunoglobulin
IGA	Investigator Global Assessment
IL	interleukin
IRB	institutional review board
ITT	intent-to-treat
IV	intravenous
LDH	Lactic dehydrogenase
LOCF	last observation carried forward
LOR	loricrin
MCH	mean corpuscular hemoglobin
MCHC	mean corpuscular hemoglobin concentration
MCMC	Markov chain Monte Carlo
MCV	mean corpuscular volume
MedDRA	Medical Dictionary for Regulatory Activities
NRS	numerical rating scale
PFS-NSD	pre-filled syringe with a pre-assembled needle safety device
PIP	proximal interphalangeal
PK	pharmacokinetics
POEM	Patient Oriented Eczema Measure
PP	per protocol
PROMIS	Patient-Reported Outcomes Measurement Information System
PUVA	psoralen (P) and ultraviolet A (UVA) therapy
Q2W	every 2 weeks
Q4W	every 4 weeks
QoL	quality of life

Acronym	Term
RBC	red blood cells
SAE	serious adverse event
SAP	statistical analysis plan
SC	subcutaneous
SCORAD	SCORing Atopic Dermatitis
SD	standard deviation
SOC	system organ class
TB	tuberculosis
TCI	topical calcineurin inhibitor
TCS	topical corticosteroid
TEAE	treatment-emergent adverse event
TSLP	thymic stromal lymphopoietin
US	United States
USP	United States Pharmacopeia
VAS	visual analog scale
WBC	white blood cells
WHO	World Health Organization

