### **Escape Arm**

Intermittent use of topical rescue medications for AD is permitted for patients who are in the Escape Arm. Patients who may require short-term systemic treatment for symptoms of AD during the Escape Arm will be assessed on a case by case basis and must be discussed with the Medical Monitor prior to initiating treatment. Patients requiring long-term systemic treatment for symptoms of AD in the Escape Arm (e.g., non-responders) must be discontinued from the study.

The Sponsor may supply the study sites with a mid-potency and a low-potency TCS that can be provided to patients for use, if needed (e.g., triamcinolone acetonide 0.1% cream and hydrocortisone 1% cream).

All topical and systemic treatments for AD must be captured in the eCRF.

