## 7.3. Week 2 ( $\pm$ 3 Days)

- Complete the following assessments: IGA, BSA and EASI
- Review and record AEs and update concomitant medication and procedure/therapy information
- Review compliance report on the eDiary, confirm moisturizer use and remind patient to record the following: Pruritus and Sleep-Loss (daily), and POEM (weekly)

- Measure vital signs
- Administer study drug

Sites collecting photos will also:

- Obtain photographs of the target lesion

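### Phototherapy counts as systemic rescue, but the SAP's search for the string 'photo' in medication names may miss entries such as PUVA or UVB (minor)

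*SAP*

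**What the plan says.** Both documents treat phototherapy as systemic rescue. Protocol 6.3 (Induction Period) names it as an example: "If systemic rescue treatments (e.g., oral corticosteroids, phototherapy, cyclosporin, etc.) are required, study drug must be discontinued". SAP Appendix 3 defines systemic AD treatment as "including systemic corticosteroids, immunosuppressant, biologics and phototherapy/photochemotherapy".

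Appendix 3 finds the other systemic classes by ATC code, by listed preferred terms, or both. Phototherapy has a different rule: "Programming search of medication name (actual term or preferred term) contains" the string 'photo', "then medicals to manually review to confirm whether the medication in question is indeed" phototherapy or photochemotherapy. No synonyms are given, and no record other than the medication name is mentioned.

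The protocol's own vocabulary is wider than that string. Exclusion criterion 5b reads "Phototherapy and photochemotherapy (PUVA) for AD", and the acronym list expands PUVA as "psoralen (P) and ultraviolet A (UVA) therapy".

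On data capture, visits from Week 2 onward (Protocol 7.3 and later) tell sites to "Review and record AEs and update concomitant medication and procedure/therapy information". Protocol 6.3 adds: "All topical and systemic treatments for AD must be captured in the eCRF". Neither passage says that phototherapy must be entered as a medication or under a name containing 'photo'.

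**The concern.** The manual review sees only what the string search returns. It can remove false hits but cannot recover a record that was never found. A treatment already on the rescue list can therefore go unrecognised because of how a site happened to write it.

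Rescue status decides how a patient's data are handled:

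- **Induction primary estimand** (SAP 6.2.1.1, 6.4.1.1): rescue sets later values to baseline, which is non-response. Discontinuation for a reason other than lack of efficacy sets them to missing, and they are multiply imputed.
- **Induction tipping-point analysis** (SAP 6.4.1.2): rescued patients are fixed as non-responders. Patients missing for other reasons have their response probability varied from 0 to 1.
- **Maintenance primary estimand** (SAP 6.2.2.1): systemic rescue is treatment failure. If it is not recognised, observed values stand.
- **Descriptive and time-to-event outputs**: rescue summaries, flares and time to first rescue (SAP 6.10.1) rest on the same definition. Systemic rescue also sets censoring for time to loss of response (Table KGAB.6.11).

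**Working it through.** The plan states no figure on this point, so there is none to reproduce. The check has three parts.

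**1. Apply the rule literally.** The SAP does not say whether the match is case-sensitive; I assume it is not.

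| Entry | Contains 'photo'? |
|---|---|
| Phototherapy | yes |
| Photochemotherapy (PUVA) | yes |
| UVB phototherapy | yes |
| PUVA | no |
| The acronym list's expansion of PUVA | no |
| UVB, NB-UVB, narrowband UVB, UVA1 | no |
| Ultraviolet light therapy; light therapy | no |

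The entries marked 'no' are found only if their coded preferred term contains 'photo'. The documents do not say how they would be coded.

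**2. Follow a missed patient.**

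- *Induction.* Protocol 6.3 requires study drug to stop. If the reason is coded lack of efficacy, later values are set to baseline anyway and nothing changes. If another reason is coded, Table KGAB.6.3 sets later values to missing and MCMC-MI fills them in. Under NRI any discontinuation is non-response, so that analysis is unaffected.
- *Maintenance.* Protocol 6.3 handles short-term systemic treatment case by case, and SAP 6.14.1 refers to drug interruption because of systemic rescue. A patient can therefore remain on study drug. If that patient also keeps EASI-50 and does not escape, values after phototherapy enter as observed. NRI gives no protection here, because nothing else marks the patient as a failure.

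**3. Size per missed patient.** The ceiling is one patient moving from certain non-responder to certain responder, that is 1/n. Under multiple imputation the contribution is the share of the 25 imputations with a response, so it is usually less.

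- Induction lebrikizumab: 400 × 2/3 ≈ 267; 1/267 = 0.37 points.
- Induction placebo: 400 × 1/3 ≈ 133; 1/133 = 0.75 points.
- Maintenance placebo: assume 48% of the 267 respond (the Phase 2b EASI-75 rate in the sample-size section) and one fifth are re-randomised to placebo (2:2:1). Then 267 × 0.48 = 128, 128/5 ≈ 26, and 1/26 = 3.8 points. An endpoint restricted to a smaller subset of responders would have a larger step per patient.

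The number of patients to multiply by is not in the documents.

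**The case against.** The strongest reply is that the rule is broader, and the safety nets better, than a quick reading suggests.

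- The search covers the preferred term as well as the actual term, and medications are coded with the WHO drug dictionary. A verbatim PUVA or UVB may well be found through its code. A reader might infer that such entries are certainly missed; the documents do not support that, only that they may be.
- A separate procedure record is an inference from the visit instructions and the schedule of procedures. Appendix 3 exempts phototherapies from its route condition, which suggests its authors expected them among the searched records. The protocol's own wording (phototherapy, photochemotherapy) also prompts sites towards terms that would be hit.
- In Induction, mandatory discontinuation, the lack-of-efficacy rule and NRI catch some cases. Imputed values for a patient with intolerable symptoms may well be mostly non-response.
- In Maintenance, the Medical Monitor must be consulted before systemic treatment starts, and loss of EASI-50 at Week 24, 32, 40 or 48 leads to the escape arm, which is set to baseline.

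All of this stands, and it limits the likely size. It does not repair the rule: none of these routes feeds a missed record back into the rescue flag, and the trial's own abbreviation for photochemotherapy fails the literal search.

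**Conclusion.** The point holds as a minor one. Appendix 3 can misclassify a listed rescue treatment, and a wider search is plainly better at almost no cost.

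The number affected is unknown and probably small. The per-patient shifts of 0.37, 0.75 and about 3.8 points are ceilings. They rest on an exact 2:1 split of 400 and, for Maintenance, on the assumed 48% response rate. A reader might multiply an assumed phototherapy rate by an assumed miss rate to obtain a count of misclassified patients. Neither rate is in the documents, so no count is given here.

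A reader might also infer that the error favours lebrikizumab. That does not follow: a missed patient can raise the response rate of whichever arm the patient is in, and misses on placebo would narrow the difference. Nothing here shows that the Week 16 conclusion would change. The small maintenance placebo group is the most sensitive place.

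**What to change.** In Appendix 3, replace the single-string rule with a case-insensitive search of verbatim and coded terms. Apply it to the concomitant-medication records and, if these are held separately, to the procedure/therapy records.

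- **Match as text strings:** photo, ultraviolet, light therapy, excimer, psoralen.
- **Match as whole words:** PUVA, UVA, UVB and UV, allowing variants such as UVA1 and NB-UVB. Whole-word matching matters because UV and UVA as bare strings also match drug names such as rosuvastatin and fluvastatin.

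Send every hit to the existing manual review, blinded to maintenance assignment, before the Week 52 lock. SAP Version 4 precedes both that lock and maintenance unblinding, so this can be done cleanly.

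For Induction, the SAP's revision history shows that the study team was already unblinded when Version 4 was approved. Re-run the search there only as a check, by reviewers without access to treatment assignment, and report any change in a patient's rescue status.

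The cost is a sentence or two in Appendix 3, a modest programming change and a few extra records to review.
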